3.1. Trial Design

A multi-centre international randomised controlled trial.

3.2. Trial Setting

University of Birmingham/academic setting, plus other international centres (UK, USA, Japan, Italy, Germany)

4. Eligibility

4.1. Inclusion Criteria

- Experienced colonoscopists: fully independent and have completed >1000 procedures
- Nurse endoscopists: fully independent colonoscopists (if applicable)
- Training colonoscopists: gastroenterology trainee in the process of training in colonoscopy
- Novice colonoscopists: junior doctors/medical students who have no experience of colonoscopy

4.2. Exclusion Criteria

- Inability to consent to take part in the study.

5. Recruitment, Consent, Enrolment and Randomisation

5.2. Consent

Consent to collect data, store the information at the University of Birmingham and publish the final data collected will be sought from all participants online prior to the collection of the pre- and post-training assessment.

The videos used will not contain any patient identifiable information and consent for their use for educational purposes has already been sought via a written consent form and have been used in other studies.

5.3. Randomisation

Participants will be randomised into either didactic face-to-face training or computer self-training module. This will take place prior to the training event and participants will be informed of which group they have been allocated on the day by using a computerized stratified randomisation sequence where a computer-generated random number will be assigned to each participant and then randomized to each arm to ensure a balanced number in both groups.

5.4. Blinding

Due to the nature of the intervention, participants cannot be blinded.

6. Trial procedures and assessments

6.1. Summary of assessments

	Enrolment	Allocation
TIMEPOINT**	At teaching sessions	
Eligibility screen	X	
Informed consent	X	
INTERVENTIONS:		
[Didactic training]	x	
[Computer based training]	x	

6.2. Schedule of Assessments

Participants who agree to take part in the study will complete a pre-training assessment prior to the training day. Assessment material will be uploaded on REDCap, hosted via the University of Birmingham. Each participant will receive a link via email to complete the assessments. Each participant will be asked to assess: Quality of video High/Low, NICE classification, SIMPLE classification, BASIC classification, High/Low confidence and Hazewinkel criteria for each video. This will be completed at least 2 weeks prior to the training day. On the training day participants will receive either didactic face-to-face feedback training or computer-based training (identical). A post-training assessment will be completed within 72 hours of training (same videos as pre-training but in a different randomised order). The website will self-populate the data in Microsoft Excel documents. Participants will then be invited to complete a final assessment at 3-4 months, which will conclude the study.

7. Data Handling and Record Keeping

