More recently Rastogi's group sought to identify which training method was more effective in prediction of diminutive polyp histology amongst trainees: didactic face to face training versus computer-based self-learning ²⁶. The participants were randomised to either receive didactic training in the form of a classroom training session or self-learning via computer-based material on characterisation of polyps using NBI. Trainees reviewed 40 videos of diminutive polyps with the histology being revealed and explained. Both groups were given a further 40 videos for testing. This study found those taught in the didactic group characterised polyps with higher confidence, but the overall performance was similar in the two groups. The accuracy and sensitivity were slightly better in the self-learning group (93.9% vs 85.7% p 0.01 and 95.0% vs 86.9%; p0.03 respectively) in those polyps assessed with high confidence. This study demonstrates that a computer-based training module can be as effective in didactic training, perhaps a reflection on the amount of online self-learning trainees are exposed to.

We aim to recruit participants to receive either didactic face-to-face training or self-directed computer based learning, whereby participants will be taught how to characterise lesions using the NICE, BASIC and SIMPLE classification. We aim to recruit trainees, novice endoscopists and experienced endoscopists to compare the different groups. Pre- and post-training assessments will be completed allowing us to examine the impact of training, which will consist of 40-60 videos (equal proportion of NBI, iScan OE and BLI) in the pre-training assessment and 40-60 videos (different set of videos but also equal proportion of NBI, iScan OE and BLI) in the post-training assessment. A follow up assessment will be completed at 6 months to assess the retention of skills and sustainability of colonic polyp characterisation using the optical diagnosis techniques. An existing library of NBI and OE-iScan videos will be used and further videos will be collected during routine colonoscopies with patients consenting for images to be used for teaching purposes.

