7.1. Source Data

The source data will be completed directly on to the forms provided to participants. This will include:

Experience: number of colonoscopies in lifetime/year, experience with NBI/iScan OE/BLI, stage of training if applicable.

Excel spreadsheets will be utilised to enter: quality of video (low/high), NICE (adenoma, hyperplastic polyp, invasive carcinoma), SIMPLE (hyperplastic, SSA, adenoma) and Hazewinkel criteria for SSA, and high/low confidence prediction.

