9.1.2. Planned Sub Group Analyses

Subgroup analysis will include didactic training vs. computer based self-learning. We will also compare the performance of predicting histology of NICE versus SIMPLE versus BASIC in all observations as well as only taking high confidence predictions. We will compare the inter-observer agreement between NICE, SIMPLE and BASIC.

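### The planned NICE, SIMPLE and BASIC comparison has no control of question order and one confidence rating per video, and Section 7.1 leaves BASIC out of the data entered

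*Combined protocol and SAP*

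**What the plan says.** Section 6.2 (Schedule of Assessments) asks each participant to give, besides video quality, "NICE classification, SIMPLE classification, BASIC classification, High/Low confidence and Hazewinkel criteria for each video". All three systems are thus applied by the same reader to the same video, and confidence appears once in the list. The only order control described in that section concerns the videos after training: "same videos as pre-training but in a different randomised order". Section 1 (Background and Rationale) states that "participants will be taught how to characterise lesions using the NICE, BASIC and SIMPLE classification", so no reader is assigned to a single system.

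Section 9.1.2 (Planned Sub Group Analyses) will "compare the performance of predicting histology of NICE versus SIMPLE versus BASIC in all observations as well as only taking high confidence predictions". It adds: "We will compare the inter-observer agreement between NICE, SIMPLE and BASIC".

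Section 7.1 (Source Data) gives the fields entered, apart from video quality, as "NICE (adenoma, hyperplastic polyp, invasive carcinoma), SIMPLE (hyperplastic, SSA, adenoma) and Hazewinkel criteria for SSA, and high/low confidence prediction". BASIC is not among them. Section 6.2 says of data transfer: "The website will self-populate the data in Microsoft Excel documents".

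**The concern.** A reader who has settled on a diagnosis under one system has that diagnosis in mind when answering under the next. Nothing in the plan separates the three answers or varies which system comes first. If the form shows the systems in a fixed order, any difference found could come from the system or from its place in the sequence. If later answers lean on the first, differences shrink, and a finding of no difference between systems would be hard to interpret. The comparison of inter-observer agreement is exposed in the same way.

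The high-confidence comparison has a separate limit. With one rating per video, the plan cannot say how each system performs on the calls that readers were confident of under that system.

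Finally, a form or dataset built from the list in 7.1 would hold no BASIC answers.

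**Working it through.** The plan gives no figure for this comparison. The sample size in Section 9.1.4 concerns the two training arms, so there is no stated number to reproduce. The check sets the sections side by side and adds one illustration.

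**1. Order.** Section 6.2 lists three systems per video and describes no separate sessions, washout, locking or randomised order of systems. With a fixed order, each of the three systems always has the same one of three positions. The effect of system and the effect of position then cannot be separated, however many videos are read. The documents do not say whether the order is fixed; they only fail to prevent it.

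**2. Carry-over (all values assumed).** Let A1 be the accuracy of the first-answered system, A2 the accuracy a later system would have if read independently, and c the share of later answers that copy the first diagnosis.

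- Observed later accuracy = c × A1 + (1 − c) × A2.
- Observed difference = (1 − c) × (A2 − A1).

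With A1 = 0.80 and A2 = 0.90, the true difference is 10 points:

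| c | Observed difference (points) |
|---|---|
| 0 | 10.0 |
| 0.25 | 0.75 × 10 = 7.5 |
| 0.50 | 0.50 × 10 = 5.0 |
| 0.75 | 0.25 × 10 = 2.5 |
| 0.90 | 0.10 × 10 = 1.0 |

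Agreement between a reader's own answers under two systems moves the other way. For independent readings with accuracies 0.80 and 0.85, it is 0.80 × 0.85 + 0.20 × 0.15 = 0.71. With copying it is c + (1 − c) × 0.71, which gives 0.78, 0.86, 0.93 and 0.97 for c = 0.25, 0.50, 0.75 and 0.90. The table shows direction and mechanism only. Nothing in the documents fixes c or the accuracies.

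**3. Confidence.** With one rating per reader and video, the high-confidence subset is the same set of readings for NICE, SIMPLE and BASIC. Accuracy within that common set can be computed for each system, so the analysis in 9.1.2 can be run. Accuracy on each system's own high-confidence calls cannot be derived from it.

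**4. BASIC.**

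| Place | BASIC included? |
|---|---|
| Section 1, training content | Yes |
| Section 6.2, ratings for each video | Yes |
| Section 7.1, fields entered | No |
| Section 9.1.2, comparisons | Yes |

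Three systems make three pairs, and two of them involve BASIC. If 7.1 were the complete field list, only NICE versus SIMPLE would remain. If 6.2 governs, all three pairs remain.

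**5. Analysis method.** The only test named in Section 9.1 is Fisher's exact test, for the two training groups. No method is given for three systems scored by the same reader on the same video.

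**The case against.** Several points stand against a stronger claim.

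- **The design is legitimate.** Scoring the same videos under all systems is an efficient paired design. This stands: the gap is the missing order control and paired analysis, not the sharing of videos.
- **The sequence is not stated.** A reader might infer that the systems are answered back to back in the order listed. Section 6.2 gives a list of items, not a form layout, so the documents leave this open.
- **BASIC may well be collected.** A reader might infer from 7.1 that there will be no BASIC data and that the three-way comparison is impossible. Section 6.2 asks for BASIC and has the website fill the spreadsheets, and 7.1 introduces its contents with non-exhaustive wording. An inconsistency is the most that can be claimed.
- **The confidence point is narrower than it may look.** It is tempting to say that the proportion of high-confidence readings cannot differ between systems. That is true of a single rating, but 9.1.2 plans no such comparison. A common subset also has a merit, because all systems are judged on the same readings. Recording confidence per system keeps much of that merit, since readings marked high under all three can still be analysed together.
- **Carry-over is of unknown size.** The systems do not share all categories: as listed in 7.1, SIMPLE has an SSA category and NICE does not, so some answers cannot simply be copied. The illustration cannot be read as an estimate.
- **The comparison is not central.** It appears only under subgroup analyses and is absent from the stated hypotheses and the sample size. This limits the importance of the point but does not remove it.

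**Conclusion.** The concern holds for the comparison of systems in 9.1.2. As written, that comparison is open to confounding with question order and to dilution by carry-over, and its high-confidence part cannot use system-specific confident calls. The confidence limit follows directly from one rating per video, which is the natural reading of 6.2. The order problem rests on the absence of any described control. The size of carry-over is unknown: over assumed copying shares of 0.25 to 0.90, a true 10-point difference would appear as 7.5 down to 1.0 points.

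The omission of BASIC from 7.1 is a contradiction to reconcile with 6.2 and 9.1.2.

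A reader might infer that the randomised comparison of training arms is biased too. The documents do not support that: the rating task is the same in both arms, so this point does not by itself favour either. Section 9.1 does not say which system supplies the predicted histology, so any change to the form should apply to both arms alike, from the first assessment onward.

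**What to change.** - **Section 6.2:** have REDCap randomise the order of the three systems for each participant and video, balanced within imaging platform (NBI, i-Scan OE, BLI), and lock each answer before the next is shown. Record high/low confidence for each system.
- **Section 7.1:** add BASIC to the fields entered, and the confidence rating for each system.
- **Section 9.1.2:** keep all answers in a paired comparison that accounts for reader and video and includes question order. Report first-scored answers alone as a sensitivity analysis.

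First-scored answers should not be the main analysis. They give up the pairing within video and two thirds of the readings: 60 / 3 = 20 per reader and system, or about 13 with 40 videos (Section 1 allows 40 to 60).

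Balance can only be approximate for one reader. Sixty videos give 60 / 3 = 20 per platform, and three systems have six possible orders, so each order occurs three times (18 videos) with two videos left over. Balancing across participants takes up the remainder.

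The cost is two more clicks per video (three confidence ratings instead of one), or 80 to 120 per assessment at 40 to 60 videos, plus a slightly more complex form and analysis. No participants or videos are added. The change must be made before the forms go live, because readings taken without order control or per-system confidence cannot be repaired later.

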7.1. Source Data

The source data will be completed directly on to the forms provided to participants. This will include:

Experience: number of colonoscopies in lifetime/year, experience with NBI/iScan OE/BLI, stage of training if applicable.

Excel spreadsheets will be utilised to enter: quality of video (low/high), NICE (adenoma, hyperplastic polyp, invasive carcinoma), SIMPLE (hyperplastic, SSA, adenoma) and Hazewinkel criteria for SSA, and high/low confidence prediction.

7.2. Data Management

Data will be collected on Microsoft excel via canvas.bham.ac.uk. Participants will be allocated an ID number (centre initials followed by participant initials). This will be anonymised.

7.3. Archiving

Data collected during this study, will be kept in locked filing cabinet at all times, any online data that is received will be stored on a secure system, which only the study team will have access too. The data will be stored for use until the findings and paper are written. After this time, it will be archived for a minimum on 10 years as per study procedure.

8. End of Trial Definition

This teaching project will be held on one day, participants will be followed up at 6 months following the training to repeat the post-training assessment. This will signal the end of the study.

9. Statistical Considerations

9.1. Statistical Analysis

Performance characteristics of the participants for diagnosing colonic neoplastic vs. non neoplastic lesions (sensitivity, specificity, NPV, PPV and accuracy) will be calculated by comparing predicted histology with actual histology for all polyps and for those diagnosed with high confidence.. These performance characteristics between the two groups (face to face classroom training vs. self-training module)will be compared using the Fisher's exact test. A P value of <0.05 will be considered to be statistically significant. *Kappa* statistic will

be used to determine inter-observer agreement in polyp video classification during the training session.

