2.2. Outcome Measures

Outcome measures will include accuracy of polyp prediction, sensitivity, specificity, positive predictive value and negative predictive value. Proportion of high confidence diagnoses will also be recorded. Kappa statistics will be used to determine interobserver agreement in polyp video classification.

3. Trial Design and Setting

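### The test between arms on high-confidence readings cannot separate diagnostic skill from confidence threshold or calibration, and can be significant when skill is equal

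*Combined protocol and SAP*

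**What the plan says.** Section 9.1, repeated in the Statistical Methodology paragraph of the trial summary, calculates the five performance measures "for all polyps and for those diagnosed with high confidence". It then says that these measures in the two training groups "will be compared using the Fisher's exact test", and adds: "A P value of <0.05 will be considered to be statistically significant". The natural reading is that both sets are tested between arms. Neither is named primary, and the high-confidence set is not limited to description.

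Under section 6.2, high or low confidence is the participant's own rating of each video. Section 2.2 treats it as an outcome: "Proportion of high confidence diagnoses will also be recorded". The plan does not ask for that proportion to be read together with the high-confidence performance measures.

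Section 1 describes an earlier randomised trial of didactic against computer-based training: "This study found those taught in the didactic group characterised polyps with higher confidence, but the overall performance was similar in the two groups". Among high-confidence readings, that trial favoured self-learning on accuracy (93.9% vs 85.7%, p 0.01) and sensitivity (95.0% vs 86.9%, p 0.03).

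**The concern.** In the post-training and follow-up assessments, the confidence rating is given after allocation and training. If one training method makes readers freer with the high-confidence label, that arm's subset takes in more of the readings that are hard to call, and its accuracy within the subset falls. The other arm is judged on a more selective subset. The arms can then differ on high-confidence accuracy although they are equally good at telling neoplastic from non-neoplastic polyps.

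The plan's own background gives reason to expect this. The cited trial shows higher confidence after didactic training, similar overall performance and lower high-confidence accuracy, which is the pattern a looser threshold would produce.

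The stakes are real because the trial hypothesises no difference between methods (sections 1.1 and 2.1) and is sized for non-inferiority (section 9.1.4). A significant high-confidence result that reflects only labelling habits would confuse that conclusion.

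The pre-training assessment is not affected. It precedes training, and participants learn their allocation on the training day (section 5.3).

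**Working it through.** The plan gives no figure for this point to reproduce: no high-confidence proportion, and no expected high-confidence accuracy.

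**Inputs from the documents.** Fisher's exact test at 0.05 (section 9.1; taken as two-sided, since sidedness is not stated for this test). 60 videos per participant and 7 participants per arm per centre (section 9.1.4), so 7 × 60 = 420 readings per arm per centre. Five countries (section 3.2).

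**Assumptions.** Overall accuracy of 75%, 80% or 85%, equal in both arms. A range of high-confidence shares, didactic vs self-learning. One centre per country, giving 5 × 420 = 2,100 readings per arm. Independent readings.

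**Model.** Equal-variance signal detection. Each reading has evidence x ~ N(h, 1), signed so that the reading is correct if x > 0. It is rated high confidence if |x| > c. Then:

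- overall accuracy = Φ(h)
- high-confidence share q = Φ(h − c) + Φ(−h − c)
- high-confidence accuracy = Φ(h − c) / q

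Only c differs between arms; skill h is the same.

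**Worked case, 80% accuracy (h = 0.8416).**

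- Share 85%: c = 0.2688, Φ(0.5728) = 0.7166, Φ(−1.1104) = 0.1334. High-confidence accuracy = 0.7166 / 0.85 = 84.3%.
- Share 55%: c = 0.8339, Φ(0.0077) = 0.5031, Φ(−1.6755) = 0.0469. High-confidence accuracy = 0.5031 / 0.55 = 91.5%.
- Gap: 7.2 points with no difference in skill.

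**Range at 80% accuracy** (gaps computed before rounding):

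| High-confidence share, didactic vs self-learning | High-confidence accuracy | Gap |
|---|---|---|
| 75% vs 70% | 86.9% vs 88.2% | 1.2 points |
| 75% vs 65% | 86.9% vs 89.3% | 2.4 points |
| 80% vs 60% | 85.6% vs 90.4% | 4.8 points |
| 85% vs 55% | 84.3% vs 91.5% | 7.2 points |

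The gap shrinks as overall accuracy rises. At 90% accuracy, 75% vs 65% gives 96.7% vs 97.9%, or 1.2 points.

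**How often Fisher's test gives p<0.05 between equally skilled arms.** Simulation over the three accuracy levels, 1,500 runs at 420 readings per arm and 600 runs at 2,100:

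| Share, didactic vs self-learning | High-confidence test, 420 per arm | High-confidence test, 2,100 per arm |
|---|---|---|
| 70% vs 70% | 3.6%–3.7% | 3.7%–5.8% |
| 75% vs 65% | 10%–14% | 36%–61% |
| 80% vs 60% | 27%–43% | 91%–99.7% |
| 85% vs 55% | 58%–80% | 100% |

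With unequal shares, 95%–100% of the significant results favoured the less confident arm. The same test on all videos was significant in 2.5%–5.3% of runs at 420 per arm and 3.2%–6.2% at 2,100, about nominal whatever the confidence gap.

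**The case against.** **The size is not known.** No section gives a high-confidence proportion, and the cited trial is reported only as showing higher confidence, with no rate. A gap of around 7 points needs a confidence difference of about 30 points; a 5-point difference produces about 1 point. This stands, and is why a range is shown. The simulated rates also ignore clustering of readings within participants, which is a separate problem with Fisher's test.

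**A difference in confidence is not established for this trial.** The cited trial enrolled trainees using NBI. This one adds consultants, nurse endoscopists and novices, and two further platforms. This stands: a difference is plausible, not certain.

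**The contrast is not meaningless.** A reader might infer that it is uninterpretable, or that randomisation is lost altogether. The documents do not support that. The high-confidence share and the share both high confidence and correct are each estimated in randomised arms, and their ratio describes how reliable high-confidence calls are after each training. PPV and NPV likewise condition on a reader's response. The contrast cannot isolate skill.

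**The cited result may be genuine.** A reader might infer that the earlier trial's 8.2-point gap (93.9 − 85.7) was only a threshold effect. The figures fit that, but they also fit poorer calibration after didactic training, which would be a real training effect. The documents cannot separate the two.

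**Safeguards are partly present.** The all-polyp comparison is planned and listed first, and the proportion of high-confidence diagnoses is recorded. This stands, but neither is made primary or tied to the high-confidence result.

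**Section 9.1.2 is a different matter.** Its phrase "as well as only taking high confidence predictions" might be read as a second instance. It concerns NICE, SIMPLE and BASIC, not the training arms. Section 6.2 lists confidence once per video; on that reading all three classifications share one high-confidence subset, so the selection described here does not arise.

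**Conclusion.** The concern holds in this form: the planned high-confidence test between arms cannot separate a difference in diagnostic skill from a difference in confidence threshold or calibration, and it can be significant when skill is equal. The direction follows whenever confidence tracks correctness. The size depends on assumed confidence shares and on the signal-detection model: roughly 1 to 7 points at 80% accuracy for confidence gaps of 5 to 30 points. At one centre's size a 10-point confidence gap yields a false positive in 10%–14% of runs; the much higher rates need larger gaps or the assumed pooled size.

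It would be too strong to say that a significant high-confidence difference can come only from a threshold shift; it may come from one. The all-polyp comparison is unaffected by this problem. This is a cheap improvement to the analysis plan, not a flaw that undermines the trial.

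**What to change.** In section 9.1, and in the matching paragraph of the trial summary:

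1. State that the comparison of arms over all videos is the inferential one.
2. Compare the arms over all videos on three proportions: high confidence and correct, high confidence and wrong, and low confidence. Do this separately within histologically neoplastic and non-neoplastic videos, so that sensitivity and specificity are covered. Read the three together. In the worked case above (all videos combined) they would be 71.7%, 13.3% and 15.0% against 50.3%, 4.7% and 45.0%: more confident correct calls and more confident errors, which shows a shift in confidence and not a gain or loss in accuracy.
3. Report high-confidence accuracy, sensitivity, specificity, PPV and NPV descriptively for each arm, beside that arm's high-confidence proportion, and state that they are not a test of training effect.

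The cost is a change of wording and one extra tabulation from data already collected. The customary high-confidence figures remain available for comparison with other studies but lose their P value.
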